13.6.1. Urine Collections for Urinalysis, Microscopy, and Biomarker Testing

Investigators should emphasize to staff and the subjects the importance of collecting fresh, high-quality urine specimens (clean-catch, mid-void, etc.) and ensuring appropriate handling and prompt analysis of the samples for urinalysis. Urine microscopy will be performed on all urine samples collected for urinalysis at investigative site visits. Because of the potential for extended transit times to the central laboratory, where possible, the urine microscopy should be performed using the site's local laboratory (where appropriate on-site testing capability exists) in lieu of the designated central laboratory. Urine microscopy should also be performed at any remote laboratory where appropriate on-site testing capability exists. If the local laboratory does not have on-site testing capability, the sample may be sent to the designated central laboratory.

Urine will be collected at all investigative site visits for analysis of uACR, β -2-microglobulin, cystatin C, uNGAL, KIM-1, and L-FABP. In addition, aliquots of urine will be frozen and shipped to the central laboratory for storage for possible future analysis of urine biomarkers.

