5.6.7. Potential Risks for Renal Effects

[REDACTED]

Monitoring of renal function will be undertaken in the study using standard measures (eg, sCr, estimated glomerular filtration rate [eGFR], and urinalysis including microscopy and biomarker analysis). Further information can be found in [Section 13.6](#). Any renal events occurring on study should be evaluated as detailed in [Section 13.9.5.3](#).

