11.2. Schedule of Assessments

The schedule of assessments for this study is presented in [Table 4](#) and procedures are described below. Where possible, it is preferred that procedures are performed in the following sequence during each clinic visit:

1. Questionnaires
2. 12-lead ECG
3. Blood pressure (BP), temperature, and pulse rate
4. Blood sampling; the preferred order for blood sampling is:

- a. Hematology
- b. Coagulation
- c. Clinical chemistry and other laboratory assessments
- d. PK blood sample

Table 4: Study Design and Schedule of Assessments

Assessment	Screening Period ^a	Baseline Visit ^b	Treatment Period (Visit Schedule)		Unscheduled Visit Following BTH (within 48 hrs or next working day)	Discontinuation of Study Drug	End of Study Assessment
	Screening Visit (Up to Day -28)	(Day 1)	Week 4 and Every 4 wks up to Wk 96 ^c (± 3 days)	Week 96 and Every 8 wks Until Wk 144 ^d (± 6 days)		Hemolysis Monitoring for at least 3 Consecutive Days ^e	3 Weeks (± 3 Days) After Last Dose of Study Drug
Informed consent ^f	X	X					
Inclusion-exclusion criteria	X	X					
Medical and medication history ^g	X	X					
Weight/height/BMI ^h	X	X	X	X			X
Physical examination ⁱ	X	X	X	X	X	X	X
ECG ^j	X	X	X	X			X
Pregnancy test (women) ^k	X	X	X	X			X
FSH test (women) ^l	X	X					
Vital signs	X	X	X	X	X	X	X
Clinical chemistry ^m /hematology/coagulation/urinalysis with microscopy ⁿ /iron, folate, vitamin B ₁₂ status labs ^o	X	X	X	X	X ^p	X ^p	X
Urine for biomarkers ^q			X	X	X	X	X

Abbreviations: AE = adverse event; BID = twice daily; BTH = breakthrough hemolysis; BMI = body mass index; ECG = electrocardiogram; FSH = follicle-stimulating hormone; FACIT = Functional Assessment of Chronic Illness Therapy; IMP = investigational medicinal product; PD = pharmacodynamic; PK = pharmacokinetic; PNH = paroxysmal nocturnal hemoglobinuria; QLQ-AA/PNH = Quality of Life Questionnaire for Patients with Aplastic Anemia/PNH; RBC = red blood cell; TSQM = Treatment Satisfaction Questionnaire for Medication; WBC = white blood cell.

- ^a Screening visit is required for subjects who have interrupted study drug for > 30 days.
- ^b The baseline visit should be within 28 days of the screening visit. For subjects directly rolling over from another BCX9930 study without treatment interruption, the final on-treatment visit in the prior BCX9930 study will be considered the baseline visit for this study.

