- ^l FSH will be measured at screening for any woman post-menopausal ≤ 2 years (this may be omitted if menopausal status was demonstrated with elevated FSH in the prior study). For women who do not undergo a screening visit, FSH may be assessed at baseline. In this case, the subject must have a negative urine pregnancy test at baseline prior to receiving study drug.
- ^m Cholesterol and triglycerides will be measured every 12 weeks up to Week 96 (ie, Weeks 36, 48, 60, 72, 84, and 96) and every 24 weeks thereafter (ie, Weeks 120 and 144).
- ⁿ Urine microscopy will be performed on urine collected at investigative site visits (and, where possible, at remote visits where the lab has appropriate on-site testing capability). Urine microscopy should be performed using the site's local laboratory (assuming appropriate on-site testing capability exists) in lieu of the central laboratory.
- ^o Weeks 48, 96, and 144 only.
- ^p Only limited hematology and clinical chemistry parameters measured as per Section 11.3.5 and Section 11.3.6.
- ^q Urine will be collected at investigative site visits (ie, excluding remote visits) and aliquots frozen for possible future analysis of urine biomarkers.
- ^r Completed at all treatment visits through Week 96 only.
- ^s Every 6 months through Week 96 only (ie, Weeks 24, 48, 72, and 96 only).

^t Though Week 96 only (ie, at Weeks 12, 24, 48, 72, and 96 only).

^u Single PK and PD sample collected 48 hours after treatment discontinuation.

^v Spot urine samples will be collected for analysis of the concentration of BCX9930 and metabolites at investigational site visits (ie, excluding remote visits).

^w The protocol-specified dosing regimen prior to this amendment was 500 mg BCX9930 BID. Under this amendment, subjects will take 400 mg BCX9930 BID. The IMP will be supplied by BioCryst as 100, 200, and/or 250 mg tablets to allow for dose adjustments if needed for the safety management of the subject.

^x BCX9930 dosing should continue following BTH.

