11.3.3. Baseline Visit (Day 1)

For all subjects, Informed Consent and Inclusion/ Exclusion criteria will be reviewed to ensure continued subject eligibility.

Before any study drug is administered the following assessments will be completed:

- Signing of ICF (if no screening visit)
- Review of inclusion and exclusion criteria and prohibited medications
- Review of medical and medication history
- Administration of questionnaires:
 - FACIT fatigue scale
 - QLQ-AA/PNH
 - TSQM
- Subject weight
- Complete physical examination
- Vital signs (BP, temperature, and pulse rate)
- 12-lead ECG
- Blood collection for clinical chemistry, hematology, and coagulation

- Blood sample for PNH clone (RBC and WBC)
- Urine pregnancy test for female subjects of child-bearing potential. A negative urine pregnancy result must be recorded in order for the subject to receive study drug.
- Urine collection for urinalysis with microscopy
- PK blood sample
- PD blood sample
- Review of concomitant medications and AEs
- Disease-specific assessments
 - Assessment of PNH symptoms (fatigue, dyspnea, chest pain/discomfort, difficulty swallowing (esophageal pain), abdominal pain, headache, erectile dysfunction, hemoglobinuria, jaundice)
 - Review of blood transfusions
- Study drug dispensing

Where possible, the questionnaires should be completed by the subject prior to other assessments (except signing of the ICF) to prevent influencing subject perceptions.

11.3.4. On-study Visits (Week 4 and every 4 weeks up to Week 96; Week 96 and every 8 weeks to Week 144)

Subjects will return to the clinic during Week 4 (Study Day 29 ± 3 days) and every 4 weeks up to Week 96 (Study Day $673, \pm 3$ days). Visits should be every 4 weeks until a subject has completed a total of 96 weeks on treatment with BCX9930 (ie, weeks in this study plus weeks in the previous study). Starting at Week 96 (Study Day $673, \pm 3$ days), subjects will return to the clinic every 8 weeks to Week 144 (Study Day $1009, \pm 6$ days).

Subjects do not need to withhold any doses on clinic days or take a dose in the clinic, unless the clinic visit falls during the subject's normal time of dosing.

The following assessments will be performed:

- Administration of questionnaires. Where possible, the questionnaires should be completed by the subject prior to other assessments:
 - FACIT fatigue scale at each visit through Week 96 only
 - TSQM questionnaire at Weeks 12, 24, 48, 72, and 96 only

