 - QLQ-AA/PNH at Weeks 24, 48, 72, and 96 only
- Targeted physical examination
- Subject weight
- Vital Signs (BP, temperature, and pulse rate)

- 12-lead ECG every 12 weeks up to Week 96 (ie, Weeks 12, 24, 36, 48, 60, 72, 84, and 96) and every 24 weeks thereafter (ie, Weeks 120 and 144)
- Blood collection for clinical chemistry, hematology, coagulation, and iron, folate, B₁₂ status labs (iron, folate, vitamin B₁₂ status labs at Weeks 48, 96, and 144 only)
- Blood sample for PNH clone (RBC and WBC)
- PK plasma sample
- PK urine collection
- PD blood sample
- Urine collection for urinalysis with microscopy and urine pregnancy test for female subjects of child-bearing potential
- Urine collection for biomarker testing
- Review of concomitant medications and AEs
- Disease-specific assessments
 - Assessment of PNH symptoms (fatigue, dyspnea, chest pain/discomfort, difficulty swallowing (esophageal pain), abdominal pain, headache, erectile dysfunction, hemoglobinuria, jaundice)
 - Review of blood transfusions
- Study drug accountability and study drug dispensing (where necessary)

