## 5.7.3. Change from Baseline

Change from baseline is calculated as (post-baseline result – baseline result). Percent change from baseline is calculated as (100 x change from baseline/baseline result). If either the baseline or the post-baseline result is missing, the change from baseline and percent change from baseline are set to missing as well. If the baseline result is 0, then the percent change from baseline is set to missing.

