## 9.2. Clinical Laboratory Evaluations

Non-PK/PD blood and urine samples will be obtained per the schedule of assessments in Table 2.

Laboratory test results and change from baseline will be summarized by panel, parameter, time point, and treatment. Laboratory results, including lab normal ranges, will be listed by treatment category, subject, parameter, and time point.

For continuous laboratory data that are reported using "<" or " $\leq$ ", a value of the number presented less one level of precision will be used for tables and figures. If the resulting value is equal to zero, the value will be adjusted by an additional level of precision. Similarly, ">" or " $\geq$ " will result in adding one at the level of precision for use in tables and figures. Actual results will be presented in the data listings. Table 6 provides example imputations.

Reported Value	Imputed Values
< 23	22
< 2.3	2.2
< 2	1
< 1	0.9*

Table 6:Example Imputation of Inequalities

< 0.23	0.22
< 0.1	0.09*
< 0.10	0.09
< 0.0200	0.0199
> 1.030	1.031
> 8	9

\*value precision adjusted

Hemoglobin and other transfusion-impacted parameters will be summarized using the rules for transfusion-impacted periods as described in Section 5.7.13.

Select lab parameters including but not limited to serum creatinine and urine albumin/creatinine ratio will be plotted versus time from Day 1 to last visit.

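### Biomarker urine is required at all site visits by Protocol 13.6.1 but is not scheduled at baseline, so five of the six renal urine biomarkers have no scheduled study-entry value

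*Protocol*

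**What the plan says.** Protocol 13.6.1 gives the general rule: "Urine will be collected at all investigative site visits for analysis of uACR", and goes on to name beta-2-microglobulin, cystatin C, uNGAL, KIM-1 and L-FABP. It also has aliquots frozen for possible later work. Footnote q to Protocol Table 4 repeats the rule and exempts only remote visits: "Urine will be collected at investigative site visits (ie, excluding remote visits) and aliquots frozen for possible future analysis of urine biomarkers".

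The schedule differs. In Protocol Table 4 the row "Urine for biomarkers" is blank at Screening and Baseline and marked in every later column. SAP Table 2 has the same pattern. The Baseline Visit list in Protocol 11.3.3 contains "Urine collection for urinalysis with microscopy" and no biomarker urine. The lists for on-study visits (11.3.4), unscheduled breakthrough-hemolysis visits (11.3.6) and the end-of-study visit (11.3.7) do carry the item "Urine collection for biomarker testing". Under Protocol 11.3.1, direct rollovers must complete the 11.3.3 items at their last parent-study visit.

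On purpose, Protocol 5.6.7 includes "urinalysis including microscopy and biomarker analysis" among the measures for monitoring renal function. On analysis, SAP 9.2 states: "Laboratory test results and change from baseline will be summarized by panel, parameter, time point, and treatment". SAP 5.7.3 adds: "If either the baseline or the post-baseline result is missing, the change from baseline and percent change from baseline are set to missing". SAP 5.12.1 imputes nothing except dates and times.

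**The concern.** The text rule and the schedule cannot both be followed at baseline. If sites follow the schedule, these biomarkers are first measured after about four weeks of dosing in this study, and the frozen aliquots start no earlier, so no stored Day 1 urine is scheduled that could be assayed later.

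Renal safety is prominent in this version of the protocol. Rising creatinine triggers extra assessments (11.3.4.1), a nephrology working group may review subjects and advise on dosing (13.9.5.3, 13.10), and acute kidney injury is reported in an expedited manner although it is considered expected (13.9.4.1). The protocol also says that PNH itself involves renal failure (5.2) and that creatinine rises for several reasons, including hemolysis (13.9.5.3). In that setting a within-subject value from study entry helps in reading a raised KIM-1 or uNGAL at the time of an event, above all an early one.

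**Working it through.** The plan gives no figure to reproduce and no power calculation applies. The check sets the passages side by side and counts.

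**1. Is baseline an investigative site visit?** Yes. For subjects with a dose interruption, Protocol 9.3 has the Day 1 dose given in the clinic. For direct rollovers, baseline is the final on-treatment visit of the parent study (7.1). Footnote q exempts remote visits only.

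**2. Where is biomarker urine scheduled?**

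| Visit | Table 4 / SAP Table 2 | Visit list in Protocol 11.3 |
|---|---|---|
| Screening | blank | not listed (11.3.2) |
| Baseline, Day 1 | blank | not listed (11.3.3) |
| Week 4 to Week 96 | marked | listed (11.3.4) |
| Week 96 to Week 144 | marked | listed (11.3.4) |
| Breakthrough hemolysis | marked | listed (11.3.6) |
| Hemolysis monitoring | marked | not listed (11.3.5) |
| End of study | marked | listed (11.3.7) |

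Five of seven columns are marked; the two blank ones are those before dosing in this study. The hemolysis-monitoring row is a second, smaller mismatch.

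**3. Which of the six analytes has another baseline source?** Protocol Table 5 lists the microalbumin to creatinine ratio in the urinalysis panel, which 11.3.3 collects at baseline, and the abbreviation list defines UACR as that ratio. SAP 9.2 plots it from Day 1. The other five appear only under the urine biomarker heading; the cystatin C among the additional tests in Table 5 is the blood assay. So 6 − 1 = 5 analytes have no scheduled study-entry value.

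**4. When is the first value?** Week 4 is Study Day 29, so 29 − 1 = 28 days after Day 1. With the ±3-day window this is Day 26 to Day 32, or 25 to 31 days after Day 1.

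**5. What follows for the analysis?** SAP 5.6 generally takes the Day 1 value as baseline. With none, SAP 5.7.3 sets change from baseline to missing, and SAP 5.12.1 offers no substitute. One route remains open: Protocol 14.3.2 uses the value reported in the prior study for direct rollovers. Whether parent studies measured these five biomarkers is not stated.

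**6. How many subjects could still gain a baseline?** Protocol 5.4 reports 15 subjects enrolled from Study 101 Part 3, against approximately 200 planned (7.2). If no one else had enrolled, about 200 − 15 = 185 could benefit. If enrollment were complete, none could. The actual number is not stated, so the range is 0 to about 185.

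**7. Effect of the change.** Analytes with a scheduled baseline go from 1 of 6 to 6 of 6 for subjects whose baseline is still to come.

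**The case against.** The best case on the other side has several parts.

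- *The contradiction is one of wording.* Protocol 13.6 says samples follow Table 4, and footnote q contrasts site visits with remote ones, so 13.6.1 can be read as meaning site rather than remote visits within that schedule. This is a fair account of how the wording arose. It does not supply a baseline sample.
- *Renal safety has baselines.* A reader might infer that change from baseline is missing for the renal risk as a whole. It is not. Serum creatinine, eGFR, the albumin/creatinine ratio and urinalysis with microscopy are all scheduled at baseline. The SAP plots creatinine and the ratio from Day 1 and plans Kaplan-Meier estimates for creatinine above ULN. The written withdrawal rule (7.4.1) and Table 6 use creatinine only.
- *A baseline sample would not show kidney status before exposure.* A reader might infer that it would separate pre-existing PNH kidney injury from drug effect. Inclusion criterion 3 means that every subject has already had BCX9930, and direct rollovers are on drug at baseline. The sample is off-drug only for subjects re-entering after an interruption.
- *Later samples are serial.* Biomarker urine is taken every 4 weeks to Week 96 and every 8 weeks thereafter, so an event after the first samples would have earlier within-subject values to compare with. The loss is greatest for early events.
- *No named table is left empty.* SAP Table 7 lists no display titled for urine biomarkers. Only the general sentence in SAP 9.2 reaches them.

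All but the first of these stand, and they limit the point. None gives the five analytes a scheduled study-entry value.

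**Conclusion.** The inconsistency is real and should be resolved. Five of the six urine biomarkers in Protocol 13.6.1 have no scheduled study-entry value in this study, and their change from baseline cannot be computed under SAP 9.2 and 5.7.3 unless, for direct rollovers, a parent-study value exists. Two of the assumptions are that sites follow Table 4 and 11.3.3 where these differ from 13.6.1, and that the general laboratory rule in SAP 9.2 is meant to cover the biomarkers.

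The documents do not support saying that no subject can have a baseline, because what the parent studies measured is not given. Nor can the gap be tied to a particular renal finding: that text is blacked out, and the link rests on the visible monitoring provisions. What is lost is a study-entry reference for supporting markers. The main renal measures are unaffected.

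**What to change.** 1. Mark "Urine for biomarkers" at the Baseline Visit, pre-dose, in Protocol Table 4 and SAP Table 2, and add the item "Urine collection for biomarker testing" to Protocol 11.3.3. Through 11.3.1 this also covers the last parent-study visit of direct rollovers.
2. Align 13.6.1 with the table by saying whether Screening is included. In the same pass, reconcile 11.3.5 with the hemolysis-monitoring column.
3. For subjects already enrolled, have the SAP name the reference sample for the five biomarkers: a parent-study value if one exists; otherwise the last sample before the first 400 mg BID dose, or the first on-study sample. Label it as such in any display and do not call it a pre-exposure baseline.
4. State in the SAP whether and where the biomarkers are summarized.

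The cost is one aliquot from urine already collected that day, plus the assays, per new enrollee. Day 1 values for subjects already enrolled cannot be recovered, and the number still to enroll is not stated.

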13.6.2. Menopause and Pregnancy Screen

FSH will be measured at screening for any woman post-menopausal ≤ 2 years (this may be omitted if menopausal status was demonstrated with elevated FSH in the prior study). For women who do not undergo a screening visit, FSH may be assessed at baseline. In this case, the subject must have a negative urine pregnancy test at baseline prior to receiving study drug.

For women of childbearing potential, a serum pregnancy test will be administered at screening. Urine pregnancy tests will be assessed at all subsequent visits. A serum pregnancy test should immediately be drawn and sent for analysis for any positive urine pregnancy test.

Urine pregnancy test kits will be provided by the central laboratory but will be result locally.

Starting at Week 100, women of childbearing potential will start performing urine pregnancy tests at home every 4 weeks (i.e., in between clinic visits). The results will be recorded by the site. If the urine pregnancy test is positive, the subject should contact the site immediately.

13.7. Monitoring for Hemolysis at Discontinuation of BCX9930

By inhibiting the alternative pathway of complement, the factor D inhibitor BCX9930 may improve hemoglobin levels by reducing the hemolysis of PNH RBCs. Thus, following discontinuation of BCX9930 treatment, subjects may be at risk of serious hemolysis.

Based on available data regarding the PK and PD of BCX9930, serious hemolysis, if it occurs, would be expected to present within days after discontinuation of therapy, therefore when subjects stop study drug therapy, either at the scheduled end of treatment or on premature discontinuation, they must be monitored for hemolysis, as described below. Samples may be analyzed at a local laboratory.

Hemolysis will be monitored by daily laboratory assessment of LDH, hemoglobin, complete blood count (CBC), and serum chemistry (serum creatinine, blood urea nitrogen [BUN]), along with vital signs and a targeted physical examination, for at least 3 consecutive days after discontinuing BCX9930. Sample(s) for PD biomarker analysis and PK will be collected 48 hours after the last dose of BCX9930.

Following the 3 days of monitoring, additional laboratory monitoring may be necessary, based upon the safety assessment of the Investigator and the Sponsor Medical Monitor.

13.8. Assessment of Breakthrough Hemolysis Episodes

It is possible that subjects may experience episodes of BTH while on study drug. Symptoms of BTH may include fatigue, hemoglobinuria, abdominal pain, dysphagia, shortness of breath, or thrombosis. Subjects who experience such symptoms should contact their study Investigator upon first awareness and should be assessed for BTH within 48 hours of this contact, or on the first working day following this contact.

Assessment of episodes of BTH will include LDH, hemoglobin, CBC, and serum chemistry (serum creatinine, BUN), along with vital signs and a targeted physical examination. In addition, sample(s) for PD and PK will be collected.

Local laboratory tests may be used for parts of hemolysis monitoring, as necessary.

13.9. Adverse Events

AEs will be assessed and recorded from the time of signing of the informed consent through the appropriate follow-up period. Full details on recording and reporting AEs are provided in Sections [13.9.3](#) and [13.9.4](#).

13.9.1. Definition of Adverse Events

13.9.1.1. Adverse Event

An AE is any untoward medical occurrence in a clinical study subject. No causal relationship with the study drug/IMP or with the clinical study itself is implied. An AE may be an unfavorable and unintended sign, symptom, syndrome, or illness that develops or worsens during the clinical study. Clinically relevant abnormal results of diagnostic procedures including abnormal laboratory findings (eg, requiring unscheduled diagnostic procedures or treatment measures, or resulting in withdrawal from the study) are considered to be AEs. Abnormal results of diagnostic procedures that are incidental or not clinically relevant are not reportable as AEs.

AEs include the following:

- AEs not previously observed in the subject that emerge during the protocol-specified AE reporting period (see Section 13.9.3).
- Findings from protocol-mandated interventions. This can include laboratory assessments performed in the clinical study. AEs should only be reported if the abnormalities are changes from baseline and are clinically significant as described above.
- Pre-existing medical conditions (other than the condition being studied) judged by the Investigator to have worsened in severity or frequency or changed in character during the protocol-specified AE reporting period.
- In addition, in this study the disease-related events of BTH and thromboembolic events will be reported as AEs, even if deemed related to the disease under investigation.

An adverse reaction is defined in ICH Harmonised Tripartite Guideline E2A as follows: all untoward and unintended responses to a study drug/IMP related to any dose administered. The definition covers also medication errors and uses outside what is foreseen in the protocol, including misuse and abuse of the product. The definition implies a reasonable possibility of a causal relationship between the event and the study drug/IMP. This means that there are facts (evidence) or arguments to suggest a causal relationship.

Surgical procedures should not be reported as AEs. The condition for which the surgery is required should be reported as the AE if it occurs or is detected during the study period. Planned surgical measures permitted by the clinical study protocol and the condition(s) leading to these measures are not AEs if the condition(s) was (were) known before the start of study treatment. In the latter case, the condition should be reported as medical history.

AEs are designated as “nonserious” or “serious.”

